7.5.6. On-Treatment ALT Flare and Post-Treatment Exacerbation of Hepatitis Management

On-Treatment ALT Flare is defined as:

- Confirmed (within 3 days of receipt of initial laboratory results) serum ALT $> 2 \times$ baseline value and $> 10 \times$ ULN, with or without associated symptoms

7.5.6.1. Management of ALT Flare in Subjects Receiving Study Medication

If laboratory results indicate elevation of ALT $> 2 \times$ baseline and $> 10 \times$ ULN, the following is recommended:

- Schedule the subject to return to the clinic as soon as possible (ideally within 3 days after initial laboratory results were drawn). During the visit, a clinical assessment of the subject will be performed. The assessment should include a physical examination and evaluation of the subject's mental status.
- Check the following laboratory parameters: serum ALT and AST, total bilirubin, INR, and serum albumin.
- If the ALT elevation is confirmed, the central clinical laboratory will conduct reflex testing for plasma HBV DNA, serology for HBV (HBsAg and HBsAb), HDV, HAV IgM, HCV, and HEV.

Based on the results of the confirmatory tests, the following treatment modifications are recommended:

Elevated Liver Enzymes, Normal or Stable relative to baseline Liver Function Tests

If ALT levels are elevated (i.e., $> 2 \times$ baseline and $> 10 \times$ ULN) with normal or stable total bilirubin and INR relative to baseline, the subject may remain on study medication and should be monitored weekly as long as ALT levels return to normal or baseline level.

During monitoring, if the ALT values remain persistently elevated, the investigator should discuss with the Gilead Medical Monitor whether the study drug should be discontinued.

For subjects with bridging fibrosis or cirrhosis, study drug discontinuation with treatment-free follow-up is to be avoided due to the potential risk of exacerbation of hepatitis in the setting of low hepatic reserve which could lead to decompensation. Subjects with bridging fibrosis or cirrhosis should be placed on commercially available HBV therapy following study drug discontinuation.

Elevated Liver Enzymes, Elevated Liver Function Tests

If ALT values are elevated (i.e., $> 2 \times$ baseline and $> 10 \times$ ULN), and total bilirubin is confirmed to be $2 \times$ baseline value, and INR is 0.5 above baseline, provided both are $> \text{ULN}$, the investigator should consider discontinuing study medication (upon discussion with the Gilead Medical Monitor, unless the safety of the subject is of immediate concern).

The subject should be monitored weekly as long as ALT, total bilirubin, and INR values remain elevated or above baseline values.

During monitoring, if the ALT values and the liver function tests remain persistently elevated, the investigator should discuss with the Gilead Medical Monitor whether the study drug should be discontinued.

For subjects with bridging fibrosis or cirrhosis, study drug discontinuation with treatment-free follow-up is to be avoided due to the potential risk of exacerbation of hepatitis in the setting of low hepatic reserve which could lead to decompensation. Subjects with bridging fibrosis or cirrhosis should be placed on commercially available HBV therapy following study drug discontinuation.

7.5.6.2. Management of Exacerbation of Hepatitis in Subjects who have Discontinued Study Medication

If laboratory results indicate (1) an ALT elevation $> 2 \times$ baseline and $> 10 \times$ ULN alone OR associated with (2) abnormal laboratory parameters suggestive of worsening hepatic function (total bilirubin $2 \times$ baseline, INR 0.5 above baseline, provided both are $> \text{ULN}$) and the subject is on no post-study therapy for HBV, the following is recommended:

- Schedule the subject to return to the clinic as soon as possible (ideally no later than 3 days after the initial laboratory values were drawn). During the visit, perform a clinical assessment of the subject.
- Check the following laboratory parameters: serum ALT and AST, total bilirubin, INR, and albumin.
- If the ALT elevation is confirmed, the central clinical laboratory will conduct reflex testing for plasma HBV DNA, serology for HBV (HBsAg and HBsAb), HDV, HAV IgM, HCV and HEV. If Plasma HBV DNA is increasing, the investigator should consider immediate initiation of approved therapy.
- The subject should be followed until laboratory parameters (ALT, total bilirubin, INR) return to normal or baseline up to a maximum of 6 months after the initial occurrence of the event.

7.5.7. Management of Potential Posterior Uveitis Cases

In a nine-month toxicology study conducted in dogs, some animals administered the highest dose of TAF (12-18mg/kg) had minimal mononuclear cell infiltration in the posterior uvea, considered secondary to general debilitation; this finding did not occur in animals given lower doses and it has not occurred in other animal studies. This pre-clinical finding has also not been observed in humans where the dose administered is lower than that given in the dog study, nor have there been reports of posterior uveitis in human clinical studies thus far. Nonetheless, if any subject develops signs or symptoms of posterior uveitis, investigators should contact the Gilead Medical Monitor to discuss the need for additional ophthalmologic evaluation including dilated funduscopy and optical coherence tomography (OCT).

7.6. Special Situations Reports

7.6.1. Definitions of Special Situations

Special situation reports include all reports of medication error, abuse, misuse, overdose, lack of effect reports and pregnancy reports regardless of an associated AE. Also includes reports of adverse reactions in infants following exposure from breastfeeding, and reports of adverse reactions associated with product complaints and reports arising from occupational exposure.

Medication error is any unintentional error in the prescribing, dispensing, or administration of a medicinal product while in the control of the health care provider, subject, or consumer.

Abuse is defined as persistent or sporadic intentional excessive use of a medicinal product by a subject.

Misuse is defined as any intentional or inappropriate use of a medicinal product that is not in accordance with the protocol instructions or the local prescribing information.

An overdose is defined as an accidental or intentional administration of a quantity of a medicinal product given per administration or cumulatively which is above the maximum recommended dose as per protocol or in the product labelling (as it applies to the daily dose of the subject in question). In cases of a discrepancy in drug accountability, overdose will be established only when it is clear that the subject has taken the excess dose(s). Overdose cannot be established when the subject cannot account for the discrepancy except in cases in which the investigator has reason to suspect that the subject has taken the additional dose(s).

Lack of effect is defined as a situation where there is apparent failure of the medicinal product or medical technology to bring about the intended beneficial effect on the individual in a defined population with a given medical problem, under ideal conditions of use.

Product complaint is defined as complaints arising from potential deviations in the manufacture, packaging, or distribution of the medicinal product.

7.6.2. Instructions for Reporting Special Situations

7.6.2.1. Instructions for Reporting Pregnancies

The investigator should report pregnancies in female study subjects that are identified after initiation of study medication and throughout the study, including the post study drug follow-up period, to the Gilead DSPH using the pregnancy report form within 24 hours of becoming aware of the pregnancy. Refer to Section 7.3 and the CRF/eCRF completion guidelines for full instructions on the mechanism of pregnancy reporting.

The pregnancy itself is not considered an AE nor is an induced elective abortion to terminate a pregnancy without medical reasons.

Any premature termination of pregnancy (e.g., a spontaneous abortion, an induced therapeutic abortion due to complications or other medical reasons) must be reported within 24 hours as an SAE. The underlying medical reason for this procedure should be recorded as the AE term.

A spontaneous abortion is always considered to be an SAE and will be reported as described in Sections 7.1.1 and 7.1.2. Furthermore, any SAE occurring as an adverse pregnancy outcome post study must be reported to Gilead DSPH.

The subject should receive appropriate monitoring and care until the conclusion of the pregnancy. The outcome should be reported to the CRO Safety Dept. using the pregnancy outcome report form. If the end of the pregnancy occurs after the study has been completed, the outcome should be reported directly to Gilead DSPH. Gilead DSPH contact information is as follows: Email: [contact] and [contact].

Refer to [Appendix 6](#) for Pregnancy Precautions, Definition for Female of Childbearing Potential, and Contraceptive Recommendations.

7.6.2.2. Reporting Other Special Situations

All other special situation reports must be reported on the special situations report form and forwarded to the CRO Safety Dept within 24 hours of the investigator becoming aware of the situation. These reports must consist of situations that involve study IMP, but do not apply to concomitant medications. Special situations involving non-Gilead concomitant medications does not need to be reported on the special situations report form, however, for special situations that result in AEs due to a non-Gilead concomitant medication, the AE should be reported on the AE form. Any inappropriate use of concomitant medications prohibited by this protocol should not be reported as “misuse,” but may be more appropriately documented as a protocol deviation.

Refer to Section 7.3 and the CRF/eCRF completion guidelines for full instructions on the mechanism of special situations reporting.

All clinical sequelae in relation to these special situation reports will be reported as AEs or SAEs at the same time using the AE CRF/eCRF and/or the SAE report form. Details of the symptoms and signs, clinical management, and outcome will be reported, when available.

8. STATISTICAL CONSIDERATIONS

8.1. Analysis Objectives and Endpoints

8.1.1. Analysis Objectives

The primary objectives of this study are:

- To compare the efficacy of tenofovir alafenamide (TAF) 25 mg QD versus tenofovir disoproxil fumarate (TDF) 300 mg QD for the treatment of HBeAg-negative, chronic hepatitis B at Week 48 in treatment-naïve and treatment-experienced subjects. The primary efficacy parameter is the proportion of subjects with plasma HBV DNA levels below 29 IU/mL.
- To compare the safety and tolerability of TAF 25 mg QD versus TDF 300 mg QD for the treatment of HBeAg-negative, chronic hepatitis B at Week 48 in treatment-naïve and treatment-experienced subjects

The key secondary safety objectives of this study are as follows:

- To compare the safety of TAF 25 mg QD versus TDF 300 mg QD as determined by the percent change from baseline in hip and spine BMD at Week 48
- To compare the safety of TAF 25 mg QD versus TDF 300 mg QD as determined by the change from baseline in serum creatinine at Week 48

Other secondary objectives of this study are as follows:

- To compare the efficacy of TAF 25 mg QD versus TDF 300 mg QD for the treatment of HBeAg-negative, chronic hepatitis B in regard to the proportion of subjects with plasma HBV DNA levels below 29 IU/mL at Weeks 96, and 144
- To compare the efficacy of TAF 25 mg QD versus TDF 300 mg QD for the treatment of HBeAg-negative, chronic hepatitis B in regard to the proportion of subjects with plasma HBV DNA levels below 29 IU/mL (target not detected) at Weeks 48, 96, and 144
- To compare the biochemical (ALT normalization) response of TAF 25 mg QD versus TDF 300 mg QD for the treatment of HBeAg-negative, chronic hepatitis B at Weeks 48, 96, and 144
- To compare the serological response (loss of HBsAg with seroconversion to anti-HBs) of TAF 25 mg QD versus TDF 300 mg QD for the treatment of HBeAg-negative, chronic hepatitis B at Weeks 48, 96, and 144

- To compare the change in fibrosis as assessed by FibroTest[®] of TAF 25 mg QD versus TDF 300 mg QD for the treatment of HBeAg-negative, chronic hepatitis B at Weeks 48, 96, and 144
- To compare the incidence of drug resistant mutations of TAF 25 mg QD versus TDF 300 mg QD at Weeks 48, 96, and 144
- To compare the change from baseline in ophthalmologic findings by fundoscopic examination of TAF 25 mg QD versus TDF 300 mg QD at Weeks 24, 48, 72, 96, and 144 in a subset of subjects
- To characterize the pharmacokinetics of TAF and tenofovir (TFV) and determine intracellular concentrations of tenofovir diphosphate (TFV-DP) within peripheral blood mononuclear cells (PBMC) in a subset of subjects receiving TAF or TDF
- To evaluate the comparative open-label efficacy, safety, and incidence of drug resistance mutations of TAF 25 mg QD from Week 144 through Week 384 in subjects initially randomized to TAF 25 mg QD and in subjects sequentially treated with TDF 300 mg QD and then switched to open-label TAF

8.1.2. Primary Endpoint

The primary efficacy endpoint is the proportion of subjects with plasma HBV DNA < 29 IU/mL at Week 48.

8.1.3. Secondary Endpoints

The key secondary safety endpoints are:

- The percent change from baseline at Week 48 in hip BMD
- The percent change from baseline at Week 48 in spine BMD
- The change from baseline at Week 48 in serum creatinine

8.1.4. Other Endpoints of Interest

- The proportion of subjects with plasma HBV DNA < 29 IU/mL at Weeks 96 and 144
- The proportion of subjects with plasma HBV DNA < 29 IU/mL (target not detected) at Weeks 48, 96, and 144
- The proportion of subjects with ALT normalization (by central laboratory and AASLD criteria) at Weeks 48, 96, and 144
- The proportion of subjects with HBsAg loss at Weeks 48, 96, 144, 240, and 384

- The proportion of subjects with HBsAg seroconversion to anti-HBs at Weeks 48, 96, 144, 240, and 384
- The change from baseline in fibrosis as assessed by FibroTest[®] at Weeks 48, 96, 144, 240 and 384
- The incidence of drug resistant mutations at Weeks 48, 96, 144, 240, and 384
- The change from baseline in ophthalmologic findings by fundoscopic examination at Weeks 24, 48, 72, 96, and 144 in a subset of subjects
- The proportion of subjects with treatment-emergent proteinuria (by dipstick) at Weeks 48, 96, 144, 240, and 384

8.2. Analysis Conventions

8.2.1. Analysis Sets

8.2.1.1. Efficacy

The primary analysis set for efficacy analysis the Full Analysis Set (FAS), defined as all randomized subjects who receive at least one dose of study drug. Subjects will be analyzed according to the randomized treatment assignment.

8.2.1.2. Safety

The primary analysis set for safety analyses is the Safety Analysis Set (SAS), defined as all randomized subjects who receive at least one dose of study drug. Subjects will be analyzed according to the treatment actually received.

All data collected during treatment will be included in the safety summaries. Data collected during treatment free follow up will be summarized or listed separately.

8.2.1.3. Pharmacokinetics

The PK analysis set will include all subjects who are randomized and have received at least one dose of study medication and for whom concentration data of any analytes of interest (eg, TAF and TFV) are available. The PK analysis set will be used for analyses of general pharmacokinetics.

The PK substudy analysis set will include all subjects who are randomized and have received at least one dose of study medication and for whom steady-state PK parameters of analytes TAF and TFV are available. The PK substudy analysis set will be used for detailed pharmacokinetics analyses.

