- To characterize the pharmacokinetics of TAF and tenofovir (TFV) and determine intracellular concentrations of tenofovir diphosphate (TFV-DP) within peripheral blood mononuclear cells (PBMC) in subjects receiving TAF or TDF
- To evaluate the comparative open-label efficacy, safety, and the incidence of drug resistance mutations of TAF 25 mg QD in subjects initially randomized to TAF 25 mg QD and in subjects sequentially treated with TDF 300 mg QD and then switched to open-label TAF 25 mg QD

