5.3. Dosage and Administration of TAF and TDF and Matched Placebos

Subjects will be randomly assigned (2:1) to receive one of the following treatments in a blinded fashion:

Treatment Arm A: 260 subjects TAF 25 mg QD and matched placebo of TDF 300 mg QD

Treatment Arm B: 130 subjects TDF 300 mg QD and matched placebo of TAF 25 mg QD

For China, approximately 150 additional subjects will be randomized 2:1 to receive either Treatment A (n = 100) or Treatment B (n = 50) for 144 weeks.

After 144 weeks of blinded randomized treatment (96 weeks under Amendment 2.1), each subject will switch to open-label TAF 25 mg QD for up to an additional 240 weeks (Week 144 through Week 384/ED). Subjects already assigned to open-label TAF 25 mg QD at Week 96 per Amendment 2.1 will continue on TAF through Week 384/ED.

It is preferred that subjects take their study drug according to a morning dosing schedule; however, evening dosing is allowable.

All study drugs should be taken at approximately the same time each day with food.

Observed in-clinic study drug dosing is required at Weeks 4 and 12 visits. Subjects who elect to dose in evening are not required to have in-clinic dosing and the single PK blood sample collection at the Week 4 and 12 visits.

Study drug should be administered after assessing adverse events and concomitant medication(s).

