6.7. Intensive Pharmacokinetic Substudy (Optional)

A PK substudy will be performed in a subset of subjects (n=16 and up to n=32) at selected study sites. Separate consent for the PK substudy is required. The substudy will include intensive PK profiling in plasma and will be conducted once at either of the Weeks 4, 8 or 12 visits.

Blood samples will be collected at 0 (\leq 30 minutes pre-dose), 5 minutes, 15 minutes, 30 minutes, 45 minutes, 1 hour, 1.5 hours, 2, 3, 4, 5, 8, 12 and 24 hours post-dose.

Subjects participating in the PK substudy should not take their dose on the morning of the PK visit. Study medication will be administered in clinic on the morning of intensive PK. Subjects who have been routinely dosing in the evening will need to switch to a morning dosing regimen at least 10 days prior to the intensive PK visit. In addition, subjects should fast (no food or drinks for a minimum of 8 hours except water for up to 1 hour) prior to the scheduled intensive PK visit

After collection of the pre-dose sample, subjects will be provided a standardized, moderate fat meal (approximately 600 cal, 27% fat; Details can be found in the PK Manual). **Within 5 minutes after consuming the standardized meal**, subjects will be dosed with TAF. Intensive PK sampling at the following time points will occur: 5, 15, 30, 45 minutes, 1, 1.5, 2, 3, 4, 5, 8, 12 and 24 hours post-dose. Subjects will be restricted from further water intake until 2 hours after and food intake until 4 hours after dosing. The date and time of the subject's previous dose will need to be collected in addition to the data at the PK substudy visit.

Details of pharmacokinetic blood sampling procedures and sample management will be documented in the Pharmacokinetic Sample Collection, Processing, Storage, and Shipment Manual.

Subjects participating in the PK substudy (at sites which can process PBMCs) will also be asked to provide a PBMC (pre-dose) sample at the time of the intensive PK substudy.

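### Read literally, the PK substudy analysis set requires parameters of both TAF and TFV, so no TDF-arm subject can enter it (minor wording correction)

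*Protocol*

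**What the plan says.** Protocol Section 8.2.1.3 defines two pharmacokinetic sets. Both require randomisation and at least one dose. They differ in the data requirement:

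- The PK analysis set, for general pharmacokinetics, takes subjects "for whom concentration data of any analytes of interest (eg, TAF and TFV) are available".
- The PK substudy analysis set takes subjects "for whom steady-state PK parameters of analytes TAF and TFV are available". Its purpose follows: "The PK substudy analysis set will be used for detailed pharmacokinetics analyses".

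The PK objective covers both drugs. Section 2 ends it with "within peripheral blood mononuclear cells (PBMC) in subjects receiving TAF or TDF", and Section 8.1.1 says "in a subset of subjects receiving TAF or TDF". SAP Section 1.1 repeats it.

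Section 5.3 gives the comparator arm as "Treatment Arm B: 130 subjects TDF 300 mg QD and matched placebo of TAF 25 mg QD". Sections 3.3 and 6.7 place the intensive visit once, at Week 4, 8 or 12, in 16 to 32 consenting subjects, and do not restrict entry by arm. The synopsis gives the substudy population as 30. Section 6.7 also states that, after the standardised meal, "subjects will be dosed with TAF"; Appendix 2 footnote l says the same.

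Section 8.7 plans descriptive statistics for TAF and TFV parameters, and lists the parameters to be derived in the intensive substudy.

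**The concern.** An analysis-set definition is an admission rule that a programmer will apply as written. This one joins two analytes with *and*, and one arm can supply only one of them. The preceding definition in the same section uses *any*, so a reader who takes the two together has reason to apply different rules.

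If the rule is applied literally, TDF-arm volunteers give 14 timed plasma samples each and then drop out of the set built to use them. The steady-state TFV parameters under TDF (Cmax, AUCtau and the others listed in Section 8.7) would then not appear in the detailed analyses, although the stated objective includes subjects receiving TDF.

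**Working it through.** The protocol attaches no power or precision figure to the substudy, so there is no planned number to reproduce. The check compares the texts and then counts the subjects affected.

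**1. Can a TDF-arm subject meet the rule?**
- Arm B takes TDF with TAF placebo (Section 5.3).
- The intensive visit is at Week 4, 8 or 12 (Section 6.7). Open-label TAF starts at Week 144, or Week 96 under Amendment 2.1 (Section 3.1). There is therefore no TAF exposure in Arm B at that visit.
- TDF is cleaved to TFV (Section 1.1). The Phase 1b tables agree: Table 1-5 reports TAF parameters for the four TAF dose groups only, while Table 1-6 reports TFV parameters for those groups and for TDF 300 mg.
- So a TDF-arm subject can have TFV parameters but not TAF parameters. Under the literal rule the number of TDF-arm subjects in the set is 0.

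**2. How many subjects would that be?**
Allocation is 2:1 (Section 5.1), so the expected TDF share of a substudy of size n is n/3, assuming that consent is unrelated to arm. The chance that no TDF subject is sampled is (2/3)^n.

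| n | Source | Expected TDF, n/3 | Chance of none, (2/3)^n |
|---|---|---|---|
| 16 | Sections 3.3, 6.7 (lower) | 5.3 | 0.0015 |
| 30 | Synopsis | 10.0 | 0.000005 |
| 32 | Sections 3.3, 6.7 (upper) | 10.7 | 0.000002 |

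TDF subjects would almost certainly be sampled. With the set redefined by treatment received, about 5, 10 or 11 of them would be expected in it.

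**3. What lies outside the rule?**
- *General PK analysis set.* One analyte is enough, so TDF subjects with TFV concentrations qualify.
- *Sparse samples.* The synopsis schedules single PK samples from Week 4 to Week 48 for all subjects, and says they may be used for population PK of TAF and TFV.
- *PBMC TFV-DP.* This is a concentration taken at the intensive visit. Section 8.2.1.3 assigns it to neither set.
- *Concentration-time plots.* Section 8.7 does not tie them to a named set.

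**4. Does the SAP change the rule?**
SAP Sections 1 and 2 limit it to the Week 48 analysis of subjects enrolled in China, and Section 3.1 defines no PK set. It neither corrects nor confirms the protocol wording. SAP Section 2 says the non-China Week 48 analysis was already done; the plan for that analysis is not among the documents.

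**The case against.** The best defence is that *TAF and TFV* is only a list of analytes. The synopsis says TAF and TFV parameters will be calculated for the substudy population as a whole, and Section 8.7 uses the phrase in the same loose way. Section 1.2.4 describes a PK substudy analysis set in the HIV Phase 2 trial and reports TFV exposure from its intensive substudy for the TAF and TDF regimens side by side. That may well be what was meant here too. But those passages say what will be calculated or was reported, whereas Section 8.2.1.3 says who is admitted. The Phase 2 trial's own definition is not shown. The defence makes the intention plausible; it does not remove the defect in the rule.

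The defence also limits the point. A reader might infer that the protocol names TDF as a PK comparator and removes it from every intensive-PK analysis, so that the contrast in TFV exposure or TFV-DP cannot be made within the trial. The documents do not support that:

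- The PK objective is to characterise and determine. Most of the other secondary objectives in Section 2 are to compare. TDF recipients are part of the PK population and are not named as a comparator.
- Section 8.7 is descriptive, with no ratio or test between arms.
- TFV-DP, the general PK analysis set and the sparse samples fall outside the rule, as shown in the working.

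Nor can one say that nothing overrides the wording, because the non-China SAP has not been seen.

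**Conclusion.** The definition is wrong as written, and the consequence is small. Applied literally, it excludes every TDF-arm substudy subject, about one third of the substudy (some 5 to 11 people), from the intensive TFV parameter summaries. That conflicts with an objective that covers subjects receiving either drug.

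The exclusion rests on reading *and* as requiring both analytes, and the count rests on consent being unrelated to arm. It does not reach the general PK analysis set, population PK or TFV-DP, and it leaves the primary, key secondary and safety analyses unaffected. Severity: minor.

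Separately, the statement in Section 6.7 and Appendix 2 footnote l that substudy subjects receive TAF at the visit does not agree with the blinded double-dummy arms in Section 5.3. It excludes nobody from an analysis, but the passages must be reconciled.

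**What to change.** - **Section 8.2.1.3:** define the PK substudy analysis set as randomised and dosed subjects with steady-state PK parameters of at least one analyte applicable to the treatment received: TAF and/or TFV in the TAF arm, TFV in the TDF arm.
- **Section 8.7:** state that TFV parameters are summarised by treatment arm and TAF parameters for the TAF arm only. It would also help to name the set used for TFV-DP.
- **Section 6.7 and Appendix 2 footnote l:** reconcile the dosing sentence with Section 5.3.
- **Non-China analysis:** check that the SAP used there did not apply the literal rule.

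The cost is a few lines of text. No extra subjects, samples or procedures are needed.
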